## **HBV**

To date, notifying donors with HBV NAT-yield infections has not been as successful as HIV notifications. In addition, tracking of this information is not currently routine in SANBS. Based on information obtained from the Reference Laboratory in Constantia Kloof with data covering a three month period January – March 2012, successful return and notification for donors with HBV-yield donations is significantly higher in Durban area compared to Johannesburg (Table 7). This is also an area with an appreciably higher burden of HBV infection. As with HIV, we believe we will be able to enroll nearly all persons who return for notification for recently acquired HBV infection into the study given that they will be on site for notification.

Table 7. HBV notification and counseling success rates, January – March 2012.

	JHB (Zone 1)	DBN (Zone 2)	Total
HBV	28	15	43
HBV returns	6	6	12
Return rate HBV	21%	40%	28%
*Untyped	6	5	11
Untyped returns	4	4	8
Total returns	10	10	20
Combined return rate	29%	50%	37%
*Most untyped yields that confirm are HBV therefore are included.			

### **4.3 Stratification or Randomization**

The study sample will include HIV and HBV cases who are recruited from among those with identified incident infection who return to SANBS for their results (anticipated to be ~50% of donors with incident infections). The study sample controls will be selected to achieve stratum-matching to HIV-cases by geographic region, age (5-year intervals), and population group from among donors who test negative for all infections (HIV, HBV, HCV, and syphilis) at randomly selected clinics.

### **4.4 Measurement**

#### **4.4.1 Schedule of Measurement**

**Risk Factor Questionnaire:** A new questionnaire for the South Africa setting has been developed in English from a template previously used in Brazil for the REDS-II study. It assesses risk exposure over two intervals; ever and within the 6 months preceding the index donation. **Appendix 7** provides content for the risk factor questionnaire. The interview will be an audio computer-assisted structured interview (ACASI) as done successfully in a previous REDS-II and current REDS-III study in Brazil. Participants will be able to read and hear the questions using

ear phones for privacy. Interviews will be conducted using portable laptops so as to provide ease of access to the study participants. The ACASI interview will be conducted in a private location, ideally at a SANBS blood centre, but we will allow the interview to be conducted at the study participants' location of preference, such as at home. We propose to use 10 laptop computers (2 per zone) which will permit simultaneous interviews at different locations throughout SANBS. It will take approximately 30-45 minutes to complete the questionnaire. Interview data will be backed-up from the laptops onto a server or dedicated desktop computer at SANBS central offices on a daily basis, and uploaded weekly via a secure FTP site to the Data Coordinating Centre.

The ACASI instrument will be developed in English only. South Africa has eleven official languages. However, producing the ACASI in multiple African languages is not possible. This study is unable to use multiple additional languages because the language that would be appropriate as a second study language to use varies in different parts of the country and also based on heritage. At minimum if multiple languages were to be used, we would require at least 3 more; Afrikaans, Zulu, and Xhosa, but still this might not meet the needs of all participants. In addition the cost and complexity of creating an ACASI application for more than one language is impossible to overcome. Please note that one of the questions on the interview captures information on the respondent's home language, so we will have a basic understanding of the first language of all cases and controls. All persons who are schooled in South Africa are required to learn English. It represents a common denominator language, making it an appropriate language for this study. English is the language that is most dominant in the media and government in South Africa, and commonly understood in the urban areas where SANBS operates. English is also the language of business in South Africa.

**Collection of index donation and routine donation testing specimens:** During the routine collection of a blood donation at SANBS, 3 specimens are taken from a sample pouch attached to the blood bag. One 9mL EDTA and two 6mL EDTA specimen tubes are collected and dispatched to the 2 Donation Testing sites. The 9mL specimen tube is used to perform the Novartis Ultrio Plus ID-NAT, one 6mL is used to perform the Abbott Prism anti-HIV, HCV and HBsAg assays and one 6mL specimen tube is used to perform the ABO and Rh blood grouping, Treponema palidum haemagglutination assay (TPHA) and atypical antibody screening tests. Descriptions of the tests used at SANBS are provided in **Appendix 5**.

Serological assays for anti-HIV, anti-HCV and HBsAg are performed in parallel with Nucleic acid testing (NAT) using Ultrio Plus in individual testing format. The serological and NAT assays used are manufactured by Abbott Diagnostics and Hologic/Novartis Diagnostics respectively. Donations found initial reactive on serology are retested in duplicate and a final screening outcome (FSO) determined as negative if both duplicate replicates are non-reactive and positive if either one of the replicates is reactive. Initial reactive NAT test results are repeated in duplicate on the Ultrio Plus assay as well as a discriminatory assay being performed for HIV

(dHIV), HBV (dHBV) and HCV (dHCV) to determine which virus is reacting. A donation that is non-reactive for all supplementary testing is classified as a Non repeatable reactive (NRR) and the unit destroyed but the donor is not notified. Any donation that has 1 or more of the supplementary tests reactive is classified as repeat reactive. If the NAT and serology are both considered repeat reactive the donor is classified as a concordant confirmed positive. If only FSO is reactive, but NAT non-reactive, an HIV Western Blot is performed for HIV and HBsAg neutralization performed for HBV. If these tests are reactive the donor is classified as a potential serology yield. Conversely If NAT is repeat reactive and the FSO is negative the donor is classified as a potential NAT yield. All potential yields are recalled to confirm the result. Concordant confirmed positives are counseled and deferred. To classify a concordant confirmed positive donation as recently acquired or longstanding, the Donation Testing department will perform a Limiting antigen (LAg) avidity assay for HIV and an anti-HBc (total) for HBV infections. All test results will be captured onto the Meditech mainframe, which is the SANBS blood establishment computer system (BECS).

**Samples for confirmatory testing.** Blood samples for follow-up testing will be collected in accordance with SANBS standard operating procedures, which place emphasis on identification of the donor and correct labeling of samples to avoid any sample mix-up. Wherever possible, follow-up appointments will be made for the donor to return for the follow-up results at the time of collecting the follow-up samples. Additional sample collection in addition to the standard tubes collected for confirmation will require the additional collection of one 9mL sample. Samples will be labeled, packed and transported according to SANBS standard operating procedures which comply with all local requirements for the transportation of bio-hazardous material. These specimens will be tested at the two donation testing centres and the results entered in to the centralized database.

**Storage of plasma:** While the routine testing is taking place the whole blood donation is processed into a red blood cell (RBC), fresh frozen plasma (FFP) and buffy coat. If any of the screening test results are positive the FFP unit is sent to the National Biorepository housed in Boksburg. If the positive donation is classified as a recent concordant positive the FFP is thawed and three 3.5mL aliquots are sampled and the remaining unit and aliquots are refrozen at -20°C. One aliquot is used to confirm that the blood in the bag is positive, one aliquot is used to determine viral load using the Abbott RT PCR and p24 antigen reactivity using Immunogenetics Innostest mAB in the Virology reference laboratory and one aliquot will be sent to the National Institute of Communicable Diseases (NICD) to have the genotype and drug resistance determined.

A FFP from a donation that is classified as a potential NAT yield will be thawed and the entire product sampled into 3.5 mL aliquots and frozen at -80°C. One aliquot will be sent to the Donation Testing laboratory for replicate testing to eliminate contamination of the index sample. One aliquot will be tested to determine p24 antigen reactivity using the

Immunogenetics mAB Innostest assay and viral load using the Abbott RT PCR assay. One aliquot will be sent to NICD for genotyping and drug resistance. The FFP from a donation classified as a potential serology yield will be thawed and sampled into 3.5mL aliquots and re frozen at -80°C. One aliquot will be sent to Donation Testing for replicate testing to estimate viral load using Probit analysis.

**Follow up samples collected from all HIV or HBV cases that return to the blood centre:** At the time that a blood donor is counseled by the MLOs a further set of specimen tubes will be collected and sent to the Donation Testing department:

- 1 x 9mL EDTA specimen tubes
- 3 x 9mL ACD/EDTA specimen tube
- 1 x 6mL EDTA/ACD specimen tube
- 1 x 6mL serum tube

**Tests performed on recent concordant follow up samples:** An initial screen will be performed on Ultrio Plus and Abbott Prism to confirm that the correct donor has presented. A viral load determination will be performed and if the plasma bag was not available at time of index donation, the tests normally performed on the index FFP will also be performed. All remaining samples will be separated and frozen for other possible studies.

**Tests performed on potential HIV NAT yield follow up samples:** A 9mL EDTA specimen tube will be tested on Ultrio Plus and Discriminatory HIV. If both of these tests are negative further replicates are performed to confirm the absence of virus before possible reinstating of the donor. One 6mL EDTA tube is used to test for Abbott anti-HIV to determine if seroconversion has occurred and p24 antigen testing is conducted. One 6mL EDTA tube is used to perform an Abbott RT PCR viral load. The 9mL ACD tube will have peripheral blood mononuclear cells (PBMC) isolated and stored in liquid nitrogen (LN2) for further studies. The remaining tubes will be used if the index FFP was not available to perform genotyping and drug resistance testing. All remaining specimen tubes will be separated and frozen and used for further SANBS replicate testing.

**Tests performed on potential HIV serology yield follow up samples:** One 9mL EDTA tube will be used to perform Ultrio Plus and dHIV. One 6mL EDTA tube will be used to perform Abbott Prism anti-HIV and western blot. A 9mL ACD sample will be used to collect PBMCs. All remaining tubes will be separated and the plasma frozen at -80°C.

**Tests performed on HBV potential yields:** One 9mL EDTA sample is used to perform Ultrio plus and dHBV and one 6mL EDTA tube is used to perform Abbott Prism HBsAg assay and anti-HBc IgM, anti-HBc total and anti-HBs titer. One 6mL EDTA sample is used to perform the Abbott RT PCR to determine viral load. A 9mL ACD tube will have peripheral blood mononuclear cells (PBMC) isolated and stored in liquid nitrogen (LN2) for further studies. The remaining tubes will

be used if the index FFP was not available to perform genotyping and drug resistance testing. All remaining specimen tubes will be separated and frozen and used for further SANBS replicate testing.

**Tests performed on HBsAg potential serology yields:** One 9mL ACD sample will be used to collect PBMC. All remaining tubes will be separated and the plasma frozen at -80°C.

#### 4.4.2 Definitions

dHIV – HIV discriminatory assay

dHBV – HBV discriminatory assay

RBC – Red blood cells

FFP – Fresh frozen plasma

EDTA - Ethylenediaminetetraacetic acid

ACD – Acid citrate dextrose

PBMC – Peripheral blood mononuclear cells

#### 4.5 Assessment and Measurement Procedures

**Detection of Recent HIV Infections by LAg Testing:** LAg avidity testing of concordant HIV RNA and anti-HIV positive donations collected during routine donation will be performed in the SANBS virology reference laboratory to determine whether the donor has recently acquired the infection or whether it is longstanding. LAg avidity incidence assays are focused on measurement of antibody avidity, which increases over time following seroconversion. Antibody avidity is believed to be more robust than antibody titer incidence assays because it is a functional property of maturing antibodies. Duong recently described two novel assays, including two-well avidity index EIA (AI-EIA) and single-well limiting antigen avidity EIA (LAg-Avidity EIA), to measure avidity of HIV antibodies. Key features of the one-well assay are: 1) use of rIDR-M, a multi-subtype recombinant protein that covers the immunodominant region (IDR) of gp41 of HIV-1, group M, 2) the limiting amount of antigen available to allow binding of only high-avidity antibodies, and 3) use of pH 3.0 buffer to further assist dissociation of low avidity antibodies.

**Detection of recent HBV infections by NAT and anti-HBc testing:** Recently infected individuals will be defined by either DNA+/HBsAg-/anti-HBc- or DNA+/HBsAg+/anti-HBc-. Each index donation is screened using NAT and HBsAg and if either or both are repeatable reactive then anti-HBc testing will be performed to eliminate HBV NAT yield occult infections or HBsAg long standing infections. The potential NAT yields will be tested using anti-HBc IgM, total and anti-HBs. The concordant DNA+/HBsAg+ will be tested using anti-HBc total alone.

**HIV-1 Clade Typing and Drug Resistance Testing:** Subtype and resistance analysis will be performed by the South Africa HIV reference laboratory as previously described. Following RNA isolation, complementary DNA will be obtained using Superscript reverse transcriptase and random primers. A nested PCR approach will be used to obtain one fragment containing the protease gene and approximately 700 base pairs of the RT gene. In the first round the primers K1/K2 will be used followed by DP10 and F2 primers. Three other sets of primers, RT4/DP16, F1/F2 and DP10/DP11, will be used for samples that are not amplified using the initial primers. All amplification products will be analyzed on a 1% ethidium bromide-stained agarose gel and purified using QIAquick PCR purification kit. To obtain sequence results for the entire amplified segment in both strands we will use at least 6 primers for sequencing each sample, including F1, F2, DP10 and DP11 primers and a new pair of primers - GABO 1 and GABO-2. Sequence data will be obtained using the ABI Prism Big Dye Terminator Cycle Sequencing Ready Reaction kit, according to manufacturer's protocol in an automated sequencer. Following phylogenetic analysis of the pro-RT region we will identify the subtype of each recently transmitted HIV-1 strain. Sequencing of the entire HIV-1 protease gene and of the RT gene through amino acid 240 will identify all mutations known to confer resistance to protease, nucleoside and non-nucleoside RT inhibitors. The only class of approved anti-HIV-1 drug resistance not detected by this analysis will be envelope gene mutations known to confer resistance to the more recently introduced HIV-1 fusion inhibitor Fuzeon™, which are not currently available in South Africa. To detect possible PCR contamination, sequences will be compared to each other using a web interface that uses the Blast program and which highlights any pair of sequences that have a percentage of similarity higher than a specific threshold (we will use 99% for pol gene).

**HBV Genotype Testing:** The INNO-LIPA HBV Genotyping assay (BioWeb, Innogenetics, Germany) is a line probe assay designed to identify HBV genotypes A to H. Extracted positive DNA is amplified using biotinylated PCR primers supplied in the assay. The outer primers will amplify part of domain B and C of the HBV polymerase gene, yielding an amplified target sequence of 409 bp. The nested PCR amplification yields an amplified sequence of 342 bp. After gel electrophoresis, detection of genotypes is performed using the nitrocellulose strips supplied. Amplified DNA is hybridized to specific oligonucleotide probes that are immobilized as parallel lines on strips. After hybridization, unhybridized DNA is washed from the strip; conjugate-streptavidin labelled with alkaline phosphatase is added and bound to any biotinylated hybrid. Incubation with substrate-BCIP/NBT chromogen results in a purple/brown precipitate. The reading card and interpretation chart supplied in the assay are used to interpret the lines on each strip. Internal negative and positive quality controls are included in each run. The negative control should have only the Conjugate Control line visible. All positive controls and positive samples should have the Conjugate Control line and Amplification Control lines visible. The INNO-LIPA HBV Genotyping assay is a SANAS accredited test.

**Objective 3 Biological characterization and evolution of incident HIV infection:** This study of incident HIV infections in South African blood donors provides a unique opportunity to

investigate the early virologic and immunologic course of HIV infection. Capturing these donors early in the course of HIV infection will allow us to prospectively monitor the time course of early HIV viremia, production of antibody, host immune response, and potential suppression of HIV infection in a small subset (elite controllers). Specifically, we propose to accomplish focused studies of dynamics of viremia and adaptive and innate immune responses based on follow-up laboratory studies of donors detected with acute HIV as well as studies of HIV Elite controllers. Because of the expected high proportion of HIV clade C infections these studies will contribute substantially to the understanding of whether clade C has a prolonged early viremic phase, and whether suppression of virus in elite controllers follows the same dynamics as for clade B. These studies are significant because differences in clade C early dynamics may account for higher infectivity in South Africa, and a better understanding of these dynamics are also relevant for clade C vaccine development.

We will obtain serum, plasma and PBMC specimens at time of enrollment and at 3 follow-up visits at 2, 3, and 6 months post-donation for CD4, viral load and cytokine profiling from the following two subsets of HIV-infected donors detected by NAT screening: i) early incident HIV infections, defined as HIV NAT+/ HIV antibody negative (N~50); and ii) HIV elite controllers defined as HIV NAT-/HIV antibody+ (N~20).

The testing of samples will be conducted in South Africa and in the US by BSRI (cell associated HIV RNA, pro-viral HIV DNA, cytokines). We will also have sufficient specimen volumes that will permit future studies and research collaborations. Consent for specimens to be stored and used for this purpose is included in the consent form (Appendix 3).

Serum, plasma and PBMC specimens obtained at enrollment and at 2, 3, and 6 month follow up will be tested as follows:

- SANBS and collaborating South African laboratories: HIV genotyping and drug resistance, CD4 lymphocyte counts and anti-HIV IgG and IgM antibody.
- BSRI virology core: quantitative cell-associated HIV RNA, pro-viral DNA, and cytokine panels. These data, together with clinical data will be used to perform Fiebig staging on all participants at each time point.

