The significance of this study is related to its three objectives: One, determination of demographic and behavioural risk factors for incident HIV and HBV hold great promise for informing targeted prevention measures by blood banks and public health authorities. The potential for identifying persons who are recently infected with both HIV and HBV also exists. In countries where the two viruses are highly endemic the rate of co-infection can be as high as 25%. In recent years, approximately 2.4 % of those SANBS blood donors with confirmed HIV or HBV infection have been co-infected. Prospective collection of incidence data allows for measurement of secular trends and the methodological approaches of behavioural and molecular surveillance we will use may also be of value to other countries with generalized HIV and HBV epidemics in Africa and Asia. Two, we will determine the viral subtype and drug resistance profile of all recently acquired HIV infections, and the genotype of recently acquired HBV infections, allowing study of viral evolution, viral fitness and pathogenicity. While we expect few HIV-HBV co-infections, persons with co-infection are known to have up to five-fold faster disease progression and so efforts to understand the epidemiology of both HIV and HBV, among individuals who are co-infected within the SANBS donor population has the potential for direct impact on public health and health care services in South Africa. In addition for HIV we will be able to determine the frequency at which drug-resistant strains are being transmitted in the population which has clear implications for changing pharmacogenetics and appropriate antiretroviral medicines. Three, evaluation of donors with recently acquired HIV infection and “elite controllers” (HIV antibody positive, ID-NAT negative infections) at multiple time points will be valuable to virologists and immunologists studying the natural history of early HIV infection. These studies will be useful in identifying appropriate HIV drug therapy regimens for this context, as well as strategies for producing an effective HIV vaccine, which has eluded 30 years of HIV research.

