#### **4.1.1 Inclusion Criteria**

For Objective 1a cases: allogeneic whole blood donors that test positive for incident HIV infection (per NAT or LAg Avidity) at a participating SANBS blood centre during the period of enrollment. For Objective 1b cases: allogeneic whole blood donors that test positive for incident HBV infection at a participating SANBS blood centre during the period of enrollment.

For Objective 1a and 1b controls: donors who successfully donated and are negative for all infections for which SANBS screens (HIV, HBV, HCV, and syphilis).

All participants must be able and willing to provide informed consent and complete the ACASI in the study language, English.

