To minimize any community rumors or individual anxieties linking the research to HIV status, recruitment scripts and study informational materials will emphasize that both HIV-positive, HBV-positive, and HIV and HBV-negative participants are being enrolled in order to identify and compare prevailing risk factors among the positive and negative groups. All donors will complete the same ACASI questionnaire.

**Objective 3 Participants:** Selected donors with incident HIV infections who were identified and enrolled during the first two years of Objective 1a and 2a recruitment will be prospectively enrolled into Objective 3 of the study. Participants in Objective 3 will be a subset of Objective 1a and 2a participants who meet eligibility criteria and are willing to participate in this objective. Elite controllers will include those identified in the first 2.5 recruitment years of the study. Donors will be consented and enrolled either during the post-test HIV counseling visit or shortly thereafter timed with Objective 1 enrollment and specimens collected on the day of enrollment and at 3 follow-up visits for CD4, viral load and cytokine profiling as well as PBMC preparations (**Consent in Appendix 4**). The total volume of blood collected at each follow-up visit will not exceed 48 mL.

**Study Locations:** The study will be located in geographic areas within the SANBS catchment where the proportion of donors with HIV and HBV infectious markers is high and where there is documented evidence of good success in notifying donors. We will conduct the study in 5 locations in 4 Provinces; Gauteng (Johannesburg and Pretoria), KwaZulu Natal (Durban), Mpumalanga Province and the Eastern Cape Province. For operational purposes, SANBS divides the Gauteng Province into 3 operational zones, namely “Egoli”, “Vaal” and “Northern”, with Johannesburg the main metropolitan area in Egoli and Pretoria the main metropolitan area in the Northern zone.

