The purpose of objective 3 is to prospectively characterize the virology, immunology and natural history of incident HIV infection among a cohort of recently infected blood donors and a small group of elite controllers in South Africa. Because of the prospective data collection, we will use longitudinal data analysis techniques that account for the clustered nature of the data. That is, there will be multiple time points for each blood donor. Possible outcome variables will represent the time course of early HIV viremia, production of antibody, host immune response, and potential suppression of HIV infection. The predictor variables will be HIV subtype, demographic variables, predictor variables identified in objective 1a, and predictor variables identified in the HIV subtype analysis in objective 2a. These analyses for this objective will be primarily descriptive but may include proportional hazards models.

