***If Study Group 3 (A7=3), Skip to Instruction After L9.***

**SECTION L - EXPOSURE AND TREATMENT**

*Study Group 1 Only (A7=1)*

**READ and HEARD:** *This is the final section of the questionnaire. It may be difficult for you to respond to these questions. Again, the responses are anonymous and will help us improve blood safety in South Africa.*

L1. Did you know your HIV status before your donation? (Choose one)

- 0 No
- 1 Yes
- 97 Don't Know
- 98 Refuse to Answer

L2. How do you think you may have become infected with HIV?

-----

L3. When do you think you may have been infected with HIV? (Year)

- \_\_\_\_\_\_ YYYY
- 2097 Don't Know (Year)
- 2098 Refuse to Answer (Year)

L4. When do you think you may have been infected with HIV? (Month) (Choose one)

- January
- February
- March
- April
- May
- June
- July
- August
- September
- October
- November
- December
- Don't Know
- Refuse to Answer

L5. Are you currently taking antiretroviral medicines, also called ARVs? (Choose one)

- 0 No
- 1 Yes skip to L7?
- 97 Don't Know
- 98 Refuse to Answer

L6. Have you taken antiretrovirals (ARVs) in the past? (Choose one)

- 0 No
- 1 Yes
- 97 Don't Know
- 98 Refuse to Answer

L7. (Ask of Women Only) If Female: Did you know you were HIV-positive prior to or during your most recent pregnancy?

- 0 No
- 1 Yes
- 96 Not applicable, never been pregnant **SKIP to After L9.**
- 97 Don't Know
- 98 Refuse to Answer

L8. (Ask of Women Only) Did you take antiretrovirals during your most recent pregnancy to try to prevent HIV transmission to your baby?

- 0 No
- 1 Yes
- 96 Not Applicable
- 97 Don't Know
- 98 Refuse to Answer

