**CURRENT MEDICAL STATUS**

B1. Since your last visit for participation in this study have you gone to your doctor or sought medical care at a clinic or hospital?

0 No **Skip to B2**

1 Yes

97 Don't Know

98 Refuse to Answer

B1a. If yes, what was the reason for seeking medical care? \_\_\_\_\_  
\_\_\_\_\_

B2. Since your last visit for participation in this study have you gone to a traditional healer?

0 No **Skip to B3**

1 Yes

97 Don't Know

98 Refuse to Answer

B2a. If yes, what was the reason for seeing the traditional healer? \_\_\_\_\_  
\_\_\_\_\_

B3. Since your last study visit have you had a cold, flu, or any other infection?

0 No **Skip to B4**

1 Yes

97 Don't Know

98 Refuse to Answer

B3a. If yes, what symptoms did you have? Please list all the symptoms you can think of such as headache, fever, body pain, chills, vomiting, diarrhea, or any other symptom that you may have had. \_\_\_\_\_  
 \_\_\_\_\_

B4. Since your last study visit have you started taking antiretroviral medicines, also known as ARVs?

- 0 No **Skip to B6**
- 1 Yes
- 97 Don't Know
- 98 Refuse to Answer

B4a. What are the names of the antiretroviral (ARV) medicines you are currently taking? \_\_\_\_\_  
 \_\_\_\_\_

To help trigger your memory, please look at the placard with pictures of medicines and then place a check mark in the box next to the medications that look like the ones you are taking:

Place ✓ if taking this medication	Medication
	AZT - Zidovudine
	ddI - Didanosine
	3TC - Lamivudine
	D4T - Stavudine
	ABC - Abacavir
	TDF - Tenofovir
	FTC - Emtricitabine
	IDV - Indinavir
	NVP - Nevirapine
	EFV - Efavirenz
	ETV - Etravirine
	ATV - Atazanavir
	LPV/r - Lopinavir/Ritonavir
	RAL - Raltegravir
	SQV - Saquinavir
	OTH - Other not pictured

B5. If yes, have you had any side effects from taking your current antiretroviral (ARV) medicines?

- 0 No
- 1 Yes
- 97 Don't Know
- 98 Refuse to Answer

B5a. If yes, what side effects did you have? Please list all the side effect you can think of, such as nausea, loss of appetite, vomiting, diarrhea, or any other symptom that you may have had. \_\_\_\_\_

B5b. Did you miss taking some or all of the doses of your current antiretroviral (ARV) medicines because of the side effects you experienced?

- 0 No
- 1 Yes
- 97 Don't Know
- 98 Refuse to Answer

B6. Are you currently taking anything else for your health such as vitamins, herbs, supplements or natural medicines?

- 0 No
- 1 Yes
- 97 Don't Know
- 98 Refuse to Answer

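### The elite-controller definition admits donors suppressed by antiretroviral treatment, and the questionnaires do not reliably identify them

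*Protocol*

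**What the plan says.** **Definition.** Section 4.5 gives "HIV elite controllers defined as HIV NAT-/HIV antibody+ (N~20". Section 3 uses the same two markers: "HIV antibody positive, ID-NAT negative infections". Infection itself is confirmed: Sections 4.2.1 and 4.4.1 require a reactive Western blot before a NAT-negative, antibody-positive HIV donor counts as a potential serology yield, and Table 1 repeats NAT, serology and Western blot at follow-up. Section 4.1.2 excludes deferred donors and allows exclusion at the investigator's discretion. It names neither ARV use nor a previous HIV diagnosis.

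**Instruments.** The Objective 3 form (Appendix 8) asks "B4. Since your last study visit have you started taking antiretroviral medicines, also known as ARVs". The answer No skips to B6, past B4a, which lists the ARVs being taken now. In the risk questionnaire (Appendix 7), Section L has "L5. Are you currently taking antiretroviral medicines, also called ARVs? (Choose one" and, at L6, past use. L1 to L8 are for Study Group 1 only. A7, which sets the group, offers HIV case, HBV case or control.

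**Enrolment.** Section 4.2.1 sends serology-only HIV positives to the standard SANBS survey. The Objective 3 text before Table 4 gives cohort members the Objective 1 computer questionnaire. Section 4.2.2 (Participant Enrollment) adds: "Participants in Objective 3 will be a subset of Objective 1a and 2a participants".

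**Analysis.** Section 4.9 lists among possible Objective 3 outcomes "host immune response, and potential suppression of HIV infection". ARV use is not among the listed predictors.

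**HIV cases for Objective 1a.** Section 4.1.1 takes "allogeneic whole blood donors that test positive for incident HIV infection (per NAT or LAg Avidity"; Section 4.5 restricts the assay: "LAg avidity testing of concordant HIV RNA and anti-HIV positive donations collected during routine donation".

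**The concern.** Negative NAT with positive antibody shows that infection is established and that RNA is below detection. It does not show why. Section 3 notes expanding antiretroviral coverage, and Appendix 5 describes plasma RNA as the measure of response to treatment, so the protocol itself supplies the alternative explanation. Section 4.5 wants to learn whether suppression in clade C elite controllers follows the dynamics seen in clade B. With about 20 participants, a few treated donors could change that description.

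The gap lies partly in what is asked. A statistical analysis plan can redefine a group from recorded data, but it cannot recover an ARV history that was never collected. That makes this a matter for the protocol and its questionnaires.

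**Working it through.** **1. Can a treated donor be recognised?** Take a donor on ARVs since before the index donation, NAT-negative and Western-blot positive.

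- Eligibility: meets both markers; no listed exclusion applies unless the donor was already deferred or the investigator uses discretion.
- Appendix 8: treatment did not start since the last study visit, so B4 is truthfully No at every visit and B4a is skipped. B6 concerns vitamins, herbs and the like.
- Appendix 7, A7 coded HIV case: L5 and L6 are asked and would show treatment, but the donor carries the incident-case code.
- Appendix 7, A7 coded otherwise: L5 and L6 are never shown.
- Standard SANBS survey, if Section 4.2.1 is followed: its content is not in the protocol.

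So detection depends on a coding choice the protocol does not make.

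**2. Do the enrolment passages agree?** Section 4.2.2 makes Objective 3 participants a subset of Objectives 1a and 2a. Objective 1a needs a NAT yield or a LAg-recent result, and LAg is run only on RNA-positive, antibody-positive donations. A NAT-negative donor can be neither, so elite controllers cannot belong to that subset. Nor can the same donor be assigned only the SANBS survey and also the study questionnaire.

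**3. The protocol's accrual figure.** Inputs: Table 4, 50% enrolment, 2.5 years, target 20. The Table 4 rows sum to 2 + 11 + 8 + 9 + 13 + 21 + 11 = 75, as printed. Expected enrolled:

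- mean of 2011 and 2012: 17 × 2.5 × 0.5 = 21.25
- 2011 to mid-2013: (13 + 21 + 11) × 0.5 = 22.5
- 2012 rate: 21 × 2.5 × 0.5 = 26.25

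The target of 20 is reproduced as feasible, counting every NAT-negative, antibody-positive donor.

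**4. After excluding treated donors.** With treated share f, expected enrolled = count × (1 − f). The documents give no f; the values are assumptions.

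| f | from 21.25 | from 22.5 | from 26.25 |
|---|---|---|---|
| 10% | 19.1 | 20.3 | 23.6 |
| 20% | 17.0 | 18.0 | 21.0 |
| 30% | 14.9 | 15.8 | 18.4 |

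Break-even for 20 is f = 1 − 20/count: 5.9%, 11.1% and 23.8%. Without exclusion, f of 10% to 50% means 2 to 10 of 20 are treated.

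**5. LAg-recent cases, for scale.** Section 4.8.1 expects about 160 LAg-recent and 50 NAT-only donations a year, so LAg cases are 160/210 = 76%. Suppose a share f of them is not recent and has control-level exposure (both assumptions). Observed case exposure is then p1 − 0.762 f (p1 − p0). Power is for two independent proportions, 300 against 900, two-sided 0.05, ignoring clustering because no intracluster correlation is given.

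| f | 0.15 vs 0.25: OR, power | 0.25 vs 0.35: OR, power |
|---|---|---|
| 0 | 1.89, 0.966 | 1.62, 0.910 |
| 10% | 1.81, 0.941 | 1.56, 0.865 |
| 20% | 1.74, 0.904 | 1.51, 0.806 |
| 30% | 1.67, 0.852 | 1.46, 0.734 |

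The first row is the plain odds ratio of the two proportions; Table 8 prints 1.94 and 1.65, from a simulation with clustering.

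**The case against.** Objective 3 is a small convenience cohort with a primarily descriptive analysis. Western blot already confirms infection. The text before Table 4 says the follow-up form covers medicines taken or initiated, which is wider than B4. If elite controllers are coded as HIV cases they do get L5 and L6, and their laboratory results still separate them from incident cases, so a shared code need not contaminate Objective 1a. Investigator discretion gives partial cover, and censoring or reclassification could be left to an analysis plan.

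Much of this is fair, but the definition still lacks an ARV condition, B4 is narrower than the stated intent, and the coding that would open Section L is not specified.

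The objection is stronger for the LAg cases. A reader might infer that they too are seriously contaminated by treated or long-diagnosed donors. The documents do not support that:

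- Donors suppressed to NAT-negative never reach the assay.
- An assumed false-recent rate of 1% to 5% would give 13 to 64 of 160: Table 6 has 753 × 2 = 1,506 positives a year, less 50 NAT-only, 22 serology-only and 160 LAg-recent, leaving 1,274. The rate is not in the documents, and it covers untreated, undiagnosed donors whom ARV questions cannot remove. Table 5 has 657 positives for the same months, which gives 11 to 54.
- The reversal of associations cited in Section 3 concerns age and marital status in one study, and age is a matching variable here.

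Requiring No at L1 for entry would also do harm. L1 asks whether the donor knew their HIV status, so Yes can mean a known negative, and true incident cases would be lost. L5 is asked at interview and can reflect treatment begun after donation.

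**Conclusion.** The point stands for elite controllers: as written, treated donors qualify, and whether they are recognised depends on an unstated coding choice. That limits what Objective 3 can say about natural control. Its size is unknown because the documents give no treated share. Under the assumptions above, 2 to 10 of 20 participants could be affected, and the accrual margin disappears once the share passes roughly 6% to 24%, depending on which Table 4 years are projected.

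A reader might take the rise from 2 elite controllers in 2007 to 21 in 2012 as evidence that treated donors are already present. It is not: the intervening counts are 11, 8, 9 and 13, and nothing in the protocol links them to treatment.

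For LAg-recent cases the assay definition can remain primary. Non-recent cases with control-level exposure would pull odds ratios towards 1, moderately over the range shown; the data already collected support a sensitivity analysis, not a new entry rule.

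**What to change.** 1. Add to the elite-controller definition that there was no ARV use at or before the index donation, and state how Don't Know and refused answers are handled.
2. Add an A7 code for elite controllers that opens the ARV items of Section L and keeps these donors out of the Objective 1a case group.
3. Reword B4 to current ARV use with a start date, so that treated follow-up time can be identified in the natural-history description.
4. Reconcile the three enrolment statements: the SANBS survey for serology-only donors (Section 4.2.1), the study questionnaire for Objective 3 (text before Table 4), and the subset statement (Section 4.2.2, Participant Enrollment).
5. For LAg-recent cases, add a sensitivity analysis that leaves out donors reporting a known HIV-positive result or ARV use before the index donation, or with an index viral load below a pre-set level. L1 should ask whether the donor knew they were HIV-positive, and L5 and L6 need start dates.

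**Cost.** Wording, one code and one skip rule; no new laboratory test. Section 4.6 makes the instruments subject to OMB approval, so the changes are cheapest before clearance. The margin over 20 elite controllers may shrink or vanish, and self-report will still miss some treated donors.
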